## APPENDIX D. ACTIVITY SCHEDULE

The following table shows the required activities across the 11 subject encounters. The individual activities are described in detail in the Operations Manual ([Appendix F](#)). Allowed modifications due to states of emergency or pandemic situations are detailed in the Operations Manual.

## Study Activities Table

Activity	Screening	Randomization/ Baseline	Week 2	Week 4	Week 6	Week 8	Week 12	Week 16	Premature Discontinuation	30-Day Follow Up Call
❑ INTERVIEWS & QUESTIONNAIRES										
Informed consent	✓									
Demographics	✓									
Medical history including disease specific history	✓									
Drug and alcohol history	✓									
Eligibility criteria	✓	✓								
TB Risk Assessment	✓									
AE assessment	✓	✓	✓	✓	✓	✓	✓	✓	✓	✓
Record prior and concomitant medication/therapy	✓	✓	✓	✓	✓	✓	✓	✓	✓	✓
Medical history update		✓								
DLQI		✓		✓			✓	✓	✓	
HADS		✓		✓				✓	✓	
Itch NRS daily diary		✓	✓	✓	✓	✓	✓	✓	✓	
PSS daily diary		✓	✓	✓	✓	✓	✓	✓	✓	
TSQM-9				✓				✓	✓	
WPAI: Psoriasis		✓		✓				✓	✓	
Dispense subject diaries		✓								
Subject diary review			✓	✓	✓	✓	✓	✓	✓	
Phone visit										✓

Activity	Screening	Randomization/ Baseline	Week 2	Week 4	Week 6	Week 8	Week 12	Week 16	Premature Discontinuation	30-Day Follow Up Call
LOCAL LABS & EXAMS										
12-lead ECG (single)	✓	✓	✓	✓	✓	✓	✓	✓	✓	
Complete physical exam (including height [at screening only] and weight)	✓	✓						✓	✓	
Vital signs	✓	✓	✓	✓	✓	✓	✓	✓	✓	
CXR	✓									
BSA	✓	✓						✓	✓	
sPGA	✓	✓	✓	✓	✓	✓	✓	✓	✓	
PASI	✓	✓	✓	✓	✓	✓	✓	✓	✓	
Urine pregnancy test (WOCBP)		✓		✓		✓	✓			
Optional: Skin biopsy			✓					✓		
Optional: Wound care after biopsy				✓		✓				
CENTRAL LABS										
Hepatitis panel	✓									
HIV test	✓									
FSH (for post-menopausal women)	✓									
TSH	✓									
TB testing (QuantiFERON-TB Gold test [or IGRA equivalent] and/or PPD skin test)	✓									
Chemistry (8 hour fast, excepting Screening)	✓	✓	✓	✓	✓	✓	✓	✓	✓	
Hematology	✓	✓	✓	✓	✓	✓	✓	✓	✓	
Urinalysis	✓	✓				✓		✓	✓	

Activity	Screening	Randomization/ Baseline	Week 2	Week 4	Week 6	Week 8	Week 12	Week 16	Premature Discontinuation	30-Day Follow Up Call
Serum pregnancy test (WOCBP)	✓							✓	✓	
Phone call reminder for dosing instructions prior to the visit			✓	✓	✓					
PK sample (Central Lab shipping and handling)			✓	✓	✓		✓	✓	✓	
Optional Biomarker Sample: whole blood DNA		✓								
Optional Biomarker sample: PBMC		✓		✓		✓		✓		
Optional Biomarker sample: whole blood transcriptomics		✓	✓	✓		✓		✓		
Optional Biomarker sample: serum, plasma		✓	✓	✓		✓		✓		
Optional Biomarker sample: whole blood leukocyte subsets		✓		✓		✓		✓		
Rx TREATMENT										
Assign study drug		✓								
Dispense study drug		✓	✓	✓	✓	✓	✓			
Review study drug adherence and perform drug accountability			✓	✓	✓	✓	✓	✓	✓	

AE = adverse event; BSA = Body Surface Area; CXR = chest x-ray; DLQI = Dermatology Life Quality Index; ECG = electrocardiogram; FSH = follicle stimulating hormone; HADS = Hospital Anxiety and Depression Scale; HIV = human immunodeficiency virus; IGRA = Interferon-Gamma Release Assay; NRS = Numeric Rating Scale; PASI = Psoriasis Area Severity Index; PBMC = peripheral blood mononuclear cells; PK = pharmacokinetic; PPD = purified protein derivative; PSS = Psoriasis Symptom Scale; sPGA = static Physician's Global Assessment; TB = tuberculosis; TSH = thyroid stimulating hormone; TSQM = Treatment Satisfaction Questionnaire for Medication; WOCBP = women of child bearing potential; WPAI = Work Productivity and Activity Impairment

## APPENDIX E. PROTOCOL SUMMARY OF CHANGES

### Previous Protocol Versions

Protocol	Date
Version 1.0	28 July 2021
Version 1.1 (Japan Only)	02 December 2021
Protocol Appendix (Japan Only)	01 November 2021

The purpose of this version is to update the following sections below.

### Summary of Protocol Changes:

- Protocol Title Page and Synopsis: Updated number of sites to approximately 50.  
**Rationale:** *To align with the number of sites currently participating.*
- Protocol Section 2.2, Benefits and Risks to Subjects: Revised Study M19-371 description to indicate that it is a single "and multiple" dose study.  
**Rationale:** *To correct the inadvertent omission.*
- Protocol Section 2.2, Benefits and Risks to Subjects: Added a paragraph regarding QT prolongation results from Study M21-560 to support the appropriateness of standard ECG eligibility criteria in Study M18-816.  
**Rationale:** *To justify the appropriateness of eligibility criteria #19, which includes exclusion of subjects with risk factors for torsade de pointes.*
- Protocol Section 2.2, Benefits and Risks to Subjects: Added a paragraph regarding results from Study M20-115, conducted in healthy volunteers to evaluate potential drug-drug interactions between cedirogant and statins at steady state.  
**Rationale:** *To provide current PK data regarding the interactions between cedirogant and studied statins to support the changes made to the daily use limits of concomitant statin in Section 5.1.*
- Protocol Section 2.2, Benefits and Risks to Subjects: Added a paragraph regarding results from Study M18-809, conducted in healthy volunteers to evaluate the modulatory effects of cedirogant on CYP enzymes.  
**Rationale:** *To provide current PK data regarding the modulatory effects of cedirogant on CYP enzymes, which provides support to the language added in Section 5.4 noting a potential decreased efficacy of concomitant CYP3A and CYP2C19 substrate medications.*
- Protocol Section 3.4, Additional Efficacy Endpoints; Operations Manual Section 3.19, Unscheduled Visits; Section 7.6, Skin Biopsy Procedure: Updated wording for the activities table to "Study Activities Table."  
**Rationale:** *Updated for consistency throughout both documents.*

- Protocol Section 3.6, Pharmacokinetic Endpoints; Operations Manual Section 3.15. Pharmacokinetic Sampling: Added ", possible metabolite(s), and if warranted, relevant concomitant medications" to plasma cedirogant concentrations.  
**Rationale:** *To provide clarification.*
- Protocol Section 3.7, Biomarker Research Endpoints: Corrected Operations Manual Section number from 3.8 to 3.16.  
**Rationale:** *To correct typographical error.*
- Protocol Section 4.1, Overall Study Design and Plan: Added "BL = baseline" to the abbreviations list for [Figure 1](#), Study Schema.  
**Rationale:** *To add missing abbreviation.*
- Protocol Section 4.2, Selection of Doses in the Study: Updated the dose language based on final data from multiple ascending dose (MAD) Study M17-238, as well as safety margin based on most recent rat and dog toxicity results.  
**Rationale:** *To update language based on final data from completed MAD and animal studies.*
- Protocol Section 5.1, Eligibility Criteria: Added "at both Screening and Baseline visits" to criterion #6.  
**Rationale:** *To provide clarification.*
- Protocol Section 5.1, Eligibility Criteria: Added "active" to describe skin disease in criterion #8.  
**Rationale:** *To provide clarification.*
- Protocol Section 5.1, Eligibility Criteria: Added "or 2 negative antigen test results at least 24 hours apart" to criterion #11.  
**Rationale:** *Updated to reflect the current protocol template language regarding COVID-19 testing.*
- Protocol Section 5.1, Eligibility Criteria; Section 5.5, Interruption/Discontinuation of Study Drug Due to COVID-19 Infection: Revised criterion #12 to "at least 10 days since first positive molecular test result have passed in asymptomatic patients or at least 10 days since recovery..."  
**Rationale:** *To align with current SARS-CoV-2 guidelines.*
- Protocol Section 5.1 Eligibility Criteria: Updated pitavastatin dose from 1 mg to 2 mg and atorvastatin dose from 20 mg to 40 mg in criterion #25.  
**Rationale:** *Pitavastatin PK is mainly affected by OATP1B1 (organic anion transporting polypeptide 1B1). An estimated < 100% increase in OATP1B1 substrate by co-administered cedirogant (375 mg QD) is expected based on the results from the statin drug-drug interaction (DDI) Study M20-115. The atorvastatin dose was adjusted based on observed 85% increase in Cmax of ortho-hydroxy atorvastatin (active metabolite of atorvastatin) by cedirogant (375 mg QD) in the statin DDI Study M20-115.*
- Protocol Section 5.1 Eligibility Criteria: Revised "cytochrome P450 (CYP) 3A" to "CYP3A" in criterion #27.  
**Rationale:** *Changed to abbreviation since already defined at first use.*

- Protocol Section [5.3](#), Prohibited Medications and Therapy: Added "including but not limited to corticosteroids, oral retinoids..." to the list of systemic non-biologic therapies for the treatment of chronic plaque psoriasis.

**Rationale:** *To provide clarification.*

- Protocol Section [5.3](#), Prohibited Medications and Therapy: Deleted "with unknown effects on CYP3A" regarding the prohibition of herbal therapies or other traditional medicines.

**Rationale:** *To ensure no potential DDI.*

- Protocol Section [5.4](#), Prior and Concomitant Therapy: Added language regarding moderate induction of CYP3A and CYP2C19 by cedirogant 375 mg QD, and the potential effects on drugs that are sensitive substrates with concomitant administration of cedirogant.

- **Rationale:** *To note a potential decreased efficacy of concomitant CYP3A and CYP2C19 substrate medications given the inductive effects of cedirogant on these two CYP enzymes observed in Study M18-809.*

- Protocol Section [5.5](#), Withdrawal of Subjects and Discontinuation of Study: Added "partially discontinue one or more treatment group(s)" regarding study termination. Added sentence to state that all subjects in the terminated arm(s) will be asked to return for a PD visit and to perform a 30-day follow-up phone call after the last dose of study drug.

**Rationale:** *To provide clarification in the event that only partial termination of the study is required.*

- Protocol Section [6.1](#), Complaints and Adverse Events: Added herpes zoster and hypersensitivity to supplemental report form table.

**Rationale:** *Herpes Zoster will be included as an additional search as an opportunistic infection as the risk is increased with subjects with psoriasis. Hypersensitivity reactions have been reported in healthy volunteer studies.*

- Protocol Section [6.2](#), Toxicity Management, Ocular Events: Expanded definition of AE ocular event to include investigator discretion when event does not meet the specified criterion of CTCAE Grade 2 or higher. Mandatory follow up with an ophthalmologist was changed from occurring within 7 days ( $\pm 1$  day) to occurring as soon as possible, but within 7 days at the latest.

**Rationale:** *Although current data demonstrates the risk of ocular toxicity with cedirogant to be low, a conservative approach for monitoring and reporting ocular AEs will be followed. Updated for consistency with Japan Only protocol amendment version 1.1.*

- Protocol [Appendix B](#), Responsibilities of the Investigator: Updated title to include ABBV-157.

**Rationale:** *Added for consistency with the title page.*

- Protocol [Appendix C](#), List of Protocol Signatories: Updated list of protocol signatories.

**Rationale:** *To reflect current personnel and roles.*

- Operations Manual Section 3.14, Tuberculosis Screening and Prophylaxis: For tuberculosis screening, added "which is the preferred testing method," to QuantiFERON-TB Gold Test (or IGRA equivalent). For tuberculosis testing, added "and the QUANTIFERON-TB Gold test should be utilized unless it is not possible or both tests are required by local regulations."

**Rationale:** *To provide clarification and clearer guidance for sites to follow.*

- Operations Manual Section 3.15, Pharmacokinetic Sampling: Added "The date and timing of the last two doses administered prior to the blood sample collection and the date and timing of the blood sample collection should be recorded to the nearest minute."

**Rationale:** *To provide clarification.*

- Operations Manual Section 7.1, Static Physician Global Assessment (sPGA): Corrected the numbering from sequential to individual score values (0 through 4) by descriptor.

**Rationale:** *To correct the typographical errors.*

- Operations Manual Section 7.2, Psoriasis Area and Severity Index (PASI) and Assessment of Total Body Surface Area: Corrected formula from "Dh" to "Dh."

**Rationale:** *To correct the typographical error.*

1.0 Introduction

This Statistical Analysis Plan (SAP) describes the statistical analyses for ABBV-157 Study M18-816 A Phase 2b, Multicenter, Randomized, Double-Blind, Placebo-Controlled, Dose-Ranging Study to Evaluate the Safety and Efficacy of Cedirogant (ABBV-157) in Adult Subjects with Moderate to Severe Psoriasis.

Study M18-816 examines the efficacy and safety of ABBV-157 in adult subjects with moderate to severe psoriasis.

The analyses of pharmacokinetic endpoints will not be covered in this SAP.

The SAP will not be updated in case of administrative changes or amendments to the protocol unless the changes impact the analysis.

Unless noted otherwise, all analyses will be performed using SAS Version 9.4 (SAS Institute Inc., Cary, NC 27513) or later under the UNIX operating system.

2.0 Study Design and Objectives

2.1 Objectives, Hypotheses and Estimands

The primary objective of this study is to assess the safety and efficacy of cedirogant versus placebo for the treatment of moderate to severe plaque psoriasis in adult subjects who are candidates for systemic therapy or phototherapy.

The primary objective of the study is to demonstrate a higher rate of subjects achieving Psoriasis Area and Severity Index (PASI) 75 (defined as $\geq 75\%$ reduction from Baseline in PASI) at Week 16 with at least one cedirogant dosing group compared to placebo in the Intent-to-Treat (ITT) population, which consists of all randomized subjects.

The primary endpoint is the achievement of PASI 75 at Week 16.

The secondary efficacy objective of the study is to demonstrate a higher rate of subjects achieving static Physicians Global Assessment (sPGA) score of clear or almost clear,

PASI 50/90/100, Psoriasis Symptoms Scale (PSS) total score of 0 for subjects with PSS>0 at Baseline, and itch Numerical Rating Scale (NRS)≥4-point improvement from Baseline for subjects with itch NRS≥4 at Baseline, at Week 16 with cedirogant compared to placebo in the ITT population.

As the study was terminated prematurely before the planned number of subjects could be randomized, all efficacy data will be summarized using descriptive summary statistics without statistical comparison or statistical testing. No hypotheses or estimands are defined for the primary and secondary efficacy endpoints.

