#### Primary Objective

The primary objective of this study is to assess the safety and efficacy of cedirogant versus placebo for the treatment of moderate to severe plaque psoriasis in adult subjects who are candidates for systemic therapy or phototherapy.

- Primary efficacy objective: The primary efficacy objective of the study is to demonstrate a higher rate of subjects achieving PASI 75 at Week 16 with cedirogant compared to placebo in the Intent-to-Treat (ITT) population, which consists of all randomized subjects (further described in Section 7.2).

The hypothesis corresponding to the primary endpoint is the proportion of subjects achieving PASI 75 at Week 16 with cedirogant is greater than that with placebo. The estimand corresponding to the primary endpoint is defined as the difference in the proportion of subjects achieving PASI 75 at Week 16, regardless of treatment discontinuation, between each of the cedirogant dose groups compared with placebo in the ITT Population.

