## 7.4 Statistical Analyses for Efficacy

---

The efficacy analysis will be conducted in the ITT Population and all statistical tests will be performed at a 2-sided significance level of 0.1. The 95% confidence interval of the treatment effect will be provided.

For categorical endpoints, comparisons will be made between each dose of cedirogant and placebo using Fisher's exact test. Non-responder imputation (NRI) incorporating multiple imputation (MI) to handle missing data due to COVID-19 (NRI-MI) will be the primary approach to handle missing values for categorical endpoints.

For continuous variables, comparisons of change and/or percent change from Baseline will be made between each dose of cedirogant and placebo based on the Mixed Model Repeated Measures (MMRM) adjusting for treatment, visit, and treatment-by-visit interaction as fixed factors, and Baseline value as a covariate. The MMRM will be the primary approach to handle missing values for continuous endpoints.

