9.0 Efficacy Analyses

9.1 General Considerations

All efficacy analyses will be conducted in the ITT Population.

The only and final analysis for the primary and secondary efficacy endpoints as well as all other efficacy endpoints will be performed after the last on-going subject completes the follow-up phone call or withdraws from the study and the database has been locked.

Descriptive summary statistics will be provided for efficacy endpoints at each visit by treatment groups based on the ITT population. There will be no statistical testing.

Categorical efficacy endpoints at each visit will be summarized by number of subjects, the number and percentage of subjects who achieve the endpoint, as well as the 95% confidence interval (CI) based on normal approximation.

Continuous efficacy endpoints at each visit and change from baseline at each visit will be summarized by descriptive summary statistics including number of subjects, mean, standard deviation, median, minimum, maximum. The 95% CI based on normal approximation will be provided for the mean change from baseline.

"Baseline" refers to the last non-missing observation before the first administration of study drug or randomization if no study drug is given.

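### The SAP keeps objectives stated against placebo but plans only within-arm summaries, dropping the treatment-effect interval that the protocol promised

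*SAP*

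**What the plan says.** **Protocol.** Under Primary Objective, "The estimand corresponding to the primary endpoint is defined as the difference in the proportion of subjects achieving PASI 75 at Week 16", for each dose against placebo, in all randomised subjects and whether or not they stay on treatment. Section 7.4 plans a test of each dose against placebo and adds: "The 95% confidence interval of the treatment effect will be provided".

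**SAP objectives.** SAP 2.1 keeps the overall aim to "assess the safety and efficacy of cedirogant versus placebo for the treatment of moderate to severe plaque psoriasis". It keeps the primary efficacy aim of a higher PASI 75 rate "with at least one cedirogant dosing group compared to placebo in the Intent-to-Treat (ITT) population", and secondary objectives of the same comparative form.

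**SAP analysis.** The same section then says that "all efficacy data will be summarized using descriptive summary statistics without statistical comparison or statistical testing", and "No hypotheses or estimands are defined for the primary and secondary efficacy endpoints". The reason given is that the study stopped before the planned number was randomised; SAP 2.2 traces the stop to a 39-week dog toxicity study. SAP 9.1 repeats: "There will be no statistical testing". For responder endpoints it gives the number of subjects, the number and percentage responding, and a normal-approximation 95% interval, by arm. For continuous endpoints it gives summary statistics by arm, and its only interval is for the mean change from baseline within an arm. Sections 9.3.2, 9.4.2 and 9.5 refer back to 9.1. Sections 9.3.3 and 9.4.3 rule out sensitivity analyses, 11.0 plans no others, and 13.0 repeats that nothing is compared.

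**The concern.** SAP 2.1 states a comparative aim and a few lines later excludes every analysis that would address it. The randomised contrast is what placebo control was chosen to provide, and it is the one efficacy quantity with no planned output. Intervals themselves were not given up, since 9.1 still computes one for each arm.

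Two things are at stake. First, anyone who wants the effect must choose a method and a set of subjects after the data are known, so different readers may publish different differences from the same tables. Second, a reader offered two arm intervals will tend to judge the effect by whether they overlap. That is not a valid guide: two 95% intervals can overlap while the 95% interval for the difference excludes zero.

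**Working it through.** **1. The plan's own figure.** Inputs from SAP 2.4: 50 per arm, 11% on placebo, a 60-point difference (so 71% on drug), two-sided 0.1, chi-squared test. For one dose against placebo, with pooled rate (0.11 + 0.71)/2 = 0.41:

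z = [0.60·√50 − 1.645·√(2·0.41·0.59)] / √(0.11·0.89 + 0.71·0.29) = (4.243 − 1.144)/0.551 = 5.62

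Power is above 99.99%, which agrees with the stated figure of more than 95%. Exact enumeration for Fisher's test also gives more than 99.99%. The sample size is not in dispute, and about 12 per arm would already give 95% power at this effect.

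**2. Does a reduced sample make the difference uninformative?** The documents do not give the number randomised, so n per arm is an assumption. At the planning rates the half-width is 1.96·√[(0.11·0.89 + 0.71·0.29)/n].

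| n per arm (assumed) | Half-width, points | 95% interval for a 60-point difference |
|---|---|---|
| 50 | 15.3 | 44.7 to 75.3 |
| 40 | 17.1 | 42.9 to 77.1 |
| 25 | 21.6 | 38.4 to 81.6 |
| 20 | 24.2 | 35.8 to 84.2 |
| 10 | 34.2 | 25.8 to 94.2 |

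At 10 per arm the Newcombe interval for 1/10 against 7/10 is wider at the low end, 17 to 81 points, and still excludes zero. Fewer subjects widen the interval but do not make it meaningless.

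**3. When do the planned arm intervals mislead?** Each arm interval is p ± 1.96·√[p(1−p)/n].

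*Planning rates.* At 50 per arm: 2.3 to 19.7% and 58.4 to 83.6%. At 25, the placebo upper limit is 23.3% and the active lower limit 53.2%; at 10, they are 30.4% and 42.9%. The intervals never overlap, so the problem does not arise at the design effect.

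*A moderate effect, assumed counts 4/40 and 12/40.* Arm intervals: 10% ± 9.3 = 0.7 to 19.3%, and 30% ± 14.2 = 15.8 to 44.2%. They overlap between 15.8 and 19.3%. For the difference, the Wilson limits are 4.0 to 23.0% on placebo and 18.1 to 45.4% on drug. Newcombe's method, using the unrounded limits, gives:

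- lower: 0.200 − √[(0.300 − 0.1807)² + (0.2305 − 0.100)²] = 0.023
- upper: 0.200 + √[(0.4543 − 0.300)² + (0.100 − 0.0396)²] = 0.366

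The interval is 2.3 to 36.6 points, which excludes zero although the arm intervals overlap.

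*The same rates at 30 per arm, 3/30 and 9/30.* Newcombe gives −0.5 to 39.0 points, which includes zero. The example therefore depends on n. It shows that overlap is an unreliable guide, not that this trial would show an effect.

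**4. What would a difference from the planned tables estimate?** SAP 9.2 makes observed cases the only approach: a subject without an evaluation at a visit is left out, and so are all values after treatment discontinuation. At Week 16 that leaves subjects still on treatment and assessed. The protocol's estimand takes everyone randomised, whatever happened to treatment, and Protocol 7.4 filled gaps mainly by non-responder imputation. These are different quantities. SAP 8.0 adds to the ambiguity by saying that data are used regardless of discontinuation, which 9.2 contradicts.

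**The case against.** The strongest reply is that nothing is lost. SAP 9.1 gives n, responder count and percentage by arm, which are all the inputs to an unadjusted difference and its interval. Randomisation was unstratified and the protocol's test was an unadjusted Fisher test, so no adjusted responder analysis is being withheld. For continuous endpoints, n, mean and standard deviation by arm give a crude mean difference. This stands. A reader might infer that the trial can no longer answer its question, but the documents do not support that; what is missing is a pre-specified estimate, with its method and population fixed.

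A second reply is that a difference from placebo in tables labelled ITT invites a randomised-effect reading that on-treatment observed cases may not support. This also stands, and it governs how the difference must be labelled.

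A third is that an interval gets read as a test. Three doses by seven responder endpoints is already 21 contrasts at Week 16, with no multiplicity control. That favours limiting the scope and withholding p-values. It does not favour omission, because the arm intervals already planned invite cruder informal testing.

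Finally, the change is disclosed: SAP 2.1, 13.0 and the version history all state it, and Protocol 7.1 leaves analysis details to the SAP. A reader who infers concealment would be wrong. But the disclosure explains why testing stopped, not why estimation stopped with it. A sentence saying that the comparative objectives are no longer addressed would cure the inconsistency but not supply the estimate.

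**Conclusion.** The point holds as a gap in planned reporting. The SAP retains comparative objectives and plans no between-arm quantity, so the treatment-effect interval promised in Protocol 7.4 is dropped. The stated reason for stopping is a preclinical finding, not efficacy results, and the stated reason for the descriptive analysis is too few subjects. Together these justify dropping tests, but not a descriptive estimate with its uncertainty.

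The practical size is moderate. No figure in the plan is wrong, and a crude difference can be derived. The overlap problem appears under assumed moderate effects (4/40 against 12/40) and not at the planning rates of 11% and 71%. All interval widths rest on assumed numbers per arm. A reader might also infer that adding a difference would restore the protocol's estimand; under SAP 9.2 it would not. The change should be made, but the integrity of the trial does not turn on it.

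**What to change.** **SAP 9.1.** For the Week 16 primary and secondary responder endpoints, add the difference from placebo for each cedirogant dose with a 95% Newcombe or Miettinen-Nurminen interval. For continuous endpoints, add the mean difference from placebo with a 95% interval. Label all of them descriptive, with no p-values and no claim of success.

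**Labelling.** Call them observed-case, on-treatment differences, and show for each arm the number contributing over the number randomised. State that SAP 9.2 makes them a different quantity from the protocol's estimand, and reconcile SAP 8.0 with 9.2 so that the label is true.

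**SAP 2.1 and 13.0.** Say that the difference from placebo is estimated and not tested.

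**Cost.** One column in each affected efficacy table and a short text edit; no new data. The downsides, to be stated with the tables, are wide intervals, no multiplicity control, and a selected observed-case population.
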